Methods to identify potential subjects: All eligible subjects presenting to the PI or a Co-PI with a diagnosis of NCCN high-very high prostate cancer or NCCN intermediate high-risk cancer with preoperative MRI evidence of ECE, SVI or N1 disease are eligible to undergo RP with adjuvant EBRT as their definitive therapy who also meet inclusion will be consented by the PI or a Co-PI. If a potential subject then expresses interest in participating in the study, the physician/surgeon will present the potential subject with an informed consent form. All aspects of the trial will be discussed with interested subjects including the voluntary nature of their participation. Adequate time will be given to the subject to ask questions related to

[Type here]

Effective Date: 10/18/2022

End Date: 10/17/2023

Protocol Title:	A Phase I Single-Arm Open Label Dose-Escalation Study of CivaSheet with Radical Prostatectomy with or without Adjuvant External Beam Radiation Therapy in Patients with High Risk Prostate Cancer
Principal Investigator Name/Contact Info:	[name]/ [contact]/ [contact]
Primary Contact Name/Contact Info	[contact] [name]
Date Revised:	7/22/2022
Study Number:	GCO#1: 16-1314

the conduct of the trial. We will not advertise for this trial. Subjects will be recruited from the clinic.

b) Inclusion and Exclusion Criteria:

- Any subject with NCCN very high or high risk adenocarcinoma of the prostate defined as $\geq T3a$, Gleason score ≥ 8 , or PSA > 20 who is eligible for RP (open or robotic) with adjuvant EBRT as an initial treatment option.
- Any subject with NCCN Intermediate Risk adenocarcinoma of the prostate defined as T2b-T2c, Gleason score 7, or PSA 10-20 who is eligible for RP (open or robotic) with adjuvant EBRT as an initial treatment option and at least one of the following adverse features present in pre-operative imaging: SVI, ECE, N1 disease.
- Subject must have had a pre-operative MRI or must obtain a pre-operative MRI to be eligible for participation in this study.
- Ability to understand and the willingness to sign a written informed consent.

Exclusion Criteria

- Any subject who has undergone prior radiation to the pelvis.
- Subjects presenting with distant metastases.
- On any investigational drug(s), androgen deprivation therapy or therapeutic device(s) within 30 days preceding screening.
- Currently taking immunosuppressants, or with poorly controlled diabetes (HbA1c > 8).

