- Subjects with prior treatment for PCa including BT, RT or hormone therapy.

c) Number of Subjects:

This is a 3+3 dose escalation design study to determine the MTD. This study will use 2 dose levels and 1-6 subjects at each dose level. The first subject enrolled at each dose level (60 and 75 Gy) will be monitored for the entire DLT window (3 months post EBRT completion) with subsequent subjects enrolled either at the same dose (if only 1 of the first 3 subsequent subjects at the given dose experiences DLT) or in the

[Type here]

Protocol Title:	A Phase I Single-Arm Open Label Dose-Escalation Study of CivaSheet with Radical Prostatectomy with or without Adjuvant External Beam Radiation Therapy in Patients with High Risk Prostate Cancer
Principal Investigator Name/Contact Info:	[name]/ [contact]/ [contact]
Primary Contact Name/Contact Info	[contact] [name]
Date Revised:	7/22/2022
Study Number:	GCO#1: 16-1314

next dose level if the preceding dose is deemed acceptable (i.e., < 33% DLT within 90 days post EBRT). If in the first subject, Grade 4-5 hematuria, fistula formation, proctitis or death occurs in the DLT window, the trial will be terminated. The total number of subjects for this single arm 3+3 trial design is therefore a minimum of 1 and a maximum of 12.

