Primary Contact Name/Contact Info	[contact] [name]									
Date Revised:	7/22/2022									
Study Number:	GCO#1: 16-1314									

	Pre-study	Day 1	Discharge (Typically Day 2)	1 Week	1 Month	6 Weeks	12 Weeks	23 Weeks	35 Weeks	Routinely for 4 years after Study completion
Assessment	X	X	X	X	X	X	X	X	X	X
Informed Consent, AE, Medical History/Medication s, Eligibility criteria, Pre-Surgical clearance (i.e., chest, EKG, etc.).	X									
Toxicity/ AE/ Complications (including DLT) Evaluations		X	X	X	X	X	X	X	X	X
X-Ray	X									
CBC	X	X	X							
Other required labs (PSA, testosterone, BMP)	X	X	X	X			X	X	X	
IIEF	X			X	X			X	X	X
MRI	X									
CT Scan			X		X		X		X	
Radical Prostatectomy + Civasheet Implant		X								
EBRT for 5 weeks						X				

Table 2. Time and events table for those undergoing RP + Civasheet implant without adjuvant EBRT.

	Pre-	Day	Discha	1	1	Routinel

[Type here]

Effective Date: 10/18/2022

End Date: 10/17/2023

Protocol Title:	A Phase I Single-Arm Open Label Dose-Escalation Study of CivaSheet with Radical Prostatectomy with or without Adjuvant External Beam Radiation Therapy in Patients with High Risk Prostate Cancer					
Principal Investigator Name/Contact Info:	[name]/ [contact]/ [contact]					
Primary Contact Name/Contact Info	[contact] [name]					
Date Revised:	7/22/2022					
Study Number:	GCO#1: 16-1314					

	study	1	age (Typically Day 2)	Week	Month	Year for 4 years after Study completion
Assessment	X	X	X	X	X	X
Informed Consent, AE, Medical History/Medication s, Eligibility criteria, Pre-Surgical clearance (i.e., chest, EKG, etc.).	X					
Toxicity/ AE/ Complications (including DLT) Evaluations		X	X	X	X	X
X-Ray	X					
CBC	X	X	X			
Other required labs (PSA, testosterone, BMP)	X	X	X	X		X
IIEF	X			X	X	X
MRI	X					
CT Scan			X		X	
Radical Prostatectomy + Civasheet Implant		X				

Assessments performed exclusively to determine eligibility for this study will be done only after obtaining informed consent. Assessments performed for clinical indications (not exclusively to determine study eligibility) may be used for baseline values even if the studies were done before informed consent was obtained.

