Subjects can be taken off the study treatment and/or study at any time at their own request, or they may be withdrawn at the discretion of the investigator for safety, behavioral or administrative reasons without the subject's consent. The reason for study removal and the date the subject was removed will be documented in the Case Report Form. The subject will be followed-up per protocol unless subject voluntarily withdraws consent from study. Reasons for discontinuation may include:

- Subject voluntarily withdraws from treatment (follow-up permitted);
- Subject withdraws consent (termination of treatment and follow-up);
- Subject is unable to comply with protocol requirements;
- Subject demonstrates disease progression (unless continued treatment with study drug is deemed appropriate at the discretion of the investigator) and hormonal therapy is required;
- Treating physician judges continuation on the study would not be in the subject's best interest;
- Development of second malignancy (except for basal cell carcinoma or squamous cell carcinoma of the skin) that requires treatment, which would interfere with this study;
- Research study is stopped;
- Subject does not meet study criteria;
- Lost to follow-up. If a research subject cannot be located to document survival after a period of 2 years, the subject may be considered "lost to follow-up." All attempts to contact the subject during the two years will be documented and approved by the Data Monitoring Committee.

[Type here]

Protocol Title:	A Phase I Single-Arm Open Label Dose-Escalation Study of CivaSheet with Radical Prostatectomy with or without Adjuvant External Beam Radiation Therapy in Patients with High Risk Prostate Cancer
Principal Investigator Name/Contact Info:	[name]/ [contact]/ [contact]
Primary Contact Name/Contact Info	[contact] [name]
Date Revised:	7/22/2022
Study Number:	GCO#1: 16-1314

If a situation arises in which the DSMC recommends termination of the study, we will terminate the study. If terminated, we will inform the IRB and research offices of termination. If terminated, we will continue to offer the standard of care for study subjects. If study termination is due to safety concerns, we will inform them by phone, mail or email of the study's status. If terminate not due to safety concerns, we will inform subjects during routine clinical visits.

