considered the MTD. Or if the highest level (75 Gy) has been reached and < 33% of subjects have experienced DLT, 75 Gy will be considered the MTD. If in the first subject treated at 75 Gy, NCI-CTCAE Grade 4 or higher hematuria, prostatitis or fistula formation occur, no additional subjects will be enrolled at 75 Gy and 60 Gy will be considered the MTD.

**Secondary:** We will describe the adverse events, toxicity and complication profile associated with Civasheet overall and at each dose when administered with RP and EBRT and also separately for those not receiving EBRT. Overall and for 60 and 75 Gy, the toxicity and complication profile associated with the Civasheet® will be assessed. Rates for surgical complications and adverse events, acute (< 90 days) and late (18 months days) GU and GI toxicity and adverse events using the NCI-CTCAE v4.0, RTOG Acute Toxicity Scale and Late Radiation Morbidity scales will be assessed. Erectile preservation and total urinary incontinence will be assessed overall and for each dose group once all subjects have completed the 6 month follow-up after EBRT. Peri- and post-operative complications associated with surgery will be assessed and graded using the Clavien-Dindo classification of surgical complications. Erectile preservation rates [IIEF score (erectile component) > 18] will be assessed, continence defined as the use of no pads will also be assessed. Binary or categorical outcomes will be described with proportion and 95% confidence intervals and continuous measures will be summarized with mean (SD) or median (IQR), as appropriate.

BCR defined as a post-prostatectomy serum PSA > 0.2 ng/ml will also be assessed for each subject. To evaluate cancer control, the Kaplan Meier-Method will be used to estimate BCR overall and for each dose group and separately for those receiving vs. not receiving EBRT once all subjects have completed the 6 months follow-up after EBRT or 6 months follow-up after Civasheet implant if no EBRT is given.

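### The BCR event is PSA alone, so a man who starts non-protocol hormonal therapy or radiotherapy before his PSA first exceeds 0.2 ng/ml stays BCR-free in the cancer-control estimate

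*SAP*

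**What the plan says.** **Event and analysis (SAP, Secondary).** The event is a PSA threshold and nothing else: "BCR defined as a post-prostatectomy serum PSA > 0.2 ng/ml will also be assessed for each subject". The purpose and method follow: "To evaluate cancer control, the Kaplan Meier-Method will be used to estimate BCR overall and for each dose group". Men with and without EBRT also get their own estimates, and the analysis waits until every man has 6 months of observation, counted from EBRT or, where none is given, from the implant. Planned adjuvant EBRT is therefore dealt with by separate estimates. Other PSA-lowering treatment is not mentioned.

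**Before entry (Protocol 3(b), Exclusion Criteria).** Two criteria apply: "On any investigational drug(s), androgen deprivation therapy or therapeutic device(s) within 30 days preceding screening" and "Subjects with prior treatment for PCa including BT, RT or hormone therapy".

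**After surgery (Protocol 3(g), repeated in 3(j)).** One of the listed possible reasons for discontinuation is "Subject demonstrates disease progression (unless continued treatment with study drug is deemed appropriate at the discretion of the investigator) and hormonal therapy is required". The same section adds: "The subject will be followed-up per protocol unless subject voluntarily withdraws consent from study". It also plans both a completers' analysis and an intent-to-treat analysis, and links neither to BCR.

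**Data capture (Protocol 3(d), Tables 1 and 2; 3(f)).** The laboratory row is "Other required labs (PSA, testosterone, BMP"). Medical history and medications are marked at the pre-study visit only. The data list in 3(f) names no start date or reason for hormonal therapy or radiotherapy begun later.

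**The concern.** PSA measures cancer control only while nothing outside the regimen is lowering it. Hormonal therapy suppresses PSA, and further radiotherapy can do so. If either starts while PSA is still at or below 0.2, the event may never be recorded, and the curve credits the trial regimen with control that other treatment produced.

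This is foreseeable here. Eligible men are high or very high risk, or intermediate risk with extracapsular extension, seminal vesicle invasion or N1 disease on imaging, and Protocol 3(g) itself expects that some may need hormonal therapy. There is no control arm, so the curve will be read on its own.

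The dose groups are also exposed for different lengths of time. The 75 Gy level opens only after the 60 Gy level is assessed, and BCR is analysed once, when the last man reaches 6 months. Men treated at 60 Gy will generally have had longer for such therapy to begin.

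**Working it through.** **1. No figure to reproduce.** The documents give no expected rate, event count or sample size for BCR.

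**2. What the stated rule does in each case** (taking BCR as time to the first PSA > 0.2):

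| Situation | Result under the plan |
|---|---|
| Other therapy starts after PSA first exceeds 0.2 | Event already counted; no distortion |
| Therapy for rising PSA or progression starts at PSA ≤ 0.2, and PSA then stays there | No event; too favourable if he would otherwise have crossed |
| Hormonal therapy starts without PSA rise or progression | No event while suppressed; too favourable only if he would otherwise have crossed |
| Removed under 3(g) for progression needing hormonal therapy | Follow-up continues unless consent is withdrawn; the SAP does not say whether later PSA values enter BCR |

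**3. Size per man.** Inputs: up to 6 men per dose level and 12 in total (Protocol 3(c)). Change in the crude proportion = 1/n.
- Dose group: 1/6 = 16.7 points. Exact 95% intervals: 0/6, 0 to 45.9%; 1/6, 0.4 to 64.1%; 2/6, 4.3 to 77.7%.
- Twelve men: 1/12 = 8.3 points. Exact 95% intervals: 0/12, 0 to 26.5%; 1/12, 0.2 to 38.5%.
- The number affected is not in the documents. If it were 0, 1, 2 or 3 of 12 (assumed), the shift would be at most 0, 8.3, 16.7 or 25.0 points.

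**4. The rule changes the Kaplan-Meier estimate.** Assumed data: six men at one dose, times from implant. One has BCR at month 6, one starts other therapy at month 4 with PSA ≤ 0.2, and four are event-free at month 9. BCR-free at month 9:
- PSA-only rule, as written: 1 − 1/6 = 83.3%.
- Censored at month 4: 1 − 1/5 = 80.0%.
- Counted as an event at month 4: (1 − 1/6) × (1 − 1/5) = 66.7%.

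With no other BCR, the three results are 100%, 100% and 83.3%.

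**5. Men without EBRT.** Protocol 3(c) expects 2 or fewer and replaces them at their dose level, so they come on top of the 6 and the 12. If there are 2, one reclassified man is 1/2 = 50 points in their own estimate. If the SAP's overall estimate includes them (it does not say), he is 1/(12 + 2) = 7.1 points there.

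**6. Can testosterone reveal hormonal therapy?** In Table 1 the last laboratory mark is at 35 weeks, which is 24 weeks after EBRT is due to end (6 + 5 = 11 weeks). The routine 4-year column is blank for that row. In Table 2 (no EBRT) it is marked. The follow-up text in 3(d) requires PSA at each visit without naming testosterone, and outside laboratory results are accepted. Testosterone would also not show further radiotherapy.

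**The case against.** The case against making much of this is substantial.

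- *Post-operative therapy is not wholly unaddressed.* The regimen in 3(c) contains no hormonal therapy, the Protocol requires conduct as approved, and 3(g) covers hormonal therapy needed at progression. That stands, so it would be wrong to say the plan ignores the matter. But 3(g) is permissive, allows investigator discretion, does not reach hormonal therapy without progression or further radiotherapy, and says nothing about BCR.
- *Informative censoring.* A reader might infer that men removed for progression are censored just as their disease advances. The documents do not support this: follow-up continues after removal, and no rule censors there. It is a risk only if the analysts choose to do so.
- *Attribution to the device.* A reader might infer that suppressed PSA would be credited to CivaSheet alone. The SAP plans description overall, by dose and by EBRT receipt, with no test and no such attribution.
- *Precision.* With 6 men the intervals dwarf a one-man shift. This limits the consequence, but it does not make the event rule right.
- *Estimand.* Counting treatment start as an event brings in clinicians' decisions, and censoring at hormonal therapy begun without PSA rise can itself be informative if higher-risk men receive it. Both points are fair. They argue for limiting the event to therapy given for rising PSA or progression, and for keeping the censored analysis as a sensitivity analysis.

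**Conclusion.** The point holds in a limited form. The SAP's event rule leaves a man BCR-free if he starts non-protocol hormonal therapy or further radiotherapy before PSA first exceeds 0.2 and PSA then stays down. The bias is favourable only for men who would otherwise have crossed; it is not automatic for every man so treated. One such man is worth 16.7 points in a full dose group of 6 and 8.3 points in 12; these denominators do not apply to men without EBRT. The number affected is unknown and the six-man example uses assumed data.

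BCR is a secondary, descriptive endpoint. DLT assessment, escalation and the MTD do not depend on it. The change is still worth making now: with no dedicated record of later therapy, the problem may not be correctable at analysis.

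**What to change.** 1. In the SAP, define the BCR event as the first of PSA > 0.2 ng/ml or the start of salvage radiotherapy or hormonal therapy given for rising PSA or progression. State that data collected after study removal are used.
2. Record the start date and reason of any non-protocol hormonal therapy or radiotherapy throughout follow-up, including for men followed by outside physicians. Do not rely on testosterone to detect it.
3. List the men given hormonal therapy without PSA rise or progression, and show a sensitivity analysis that censors them when it starts.

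The cost is a short SAP amendment, one added CRF field and a BCR-free figure that may be less favourable. These are recording and analysis rules only; patient care does not change.

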90 Days after Completion of EBRT

- Assessment of cumulative DLT's to decide whether progression to next dose or termination of study is necessary.

Follow-Up:

- Subjects will be followed every 6 months after completion of study treatment for 4 years or if the subject withdraws consent from participation, the subject will not be followed-up. Subjects may be followed-up by telephone or contacted by phone to schedule Mount Sinai office visits to monitor for cancer recurrence and or cancer progression in addition to late toxicity.
- Subjects will be followed yearly after completion of study treatment for 4 years or if the subject withdraws consent from participation, the subject will not be followed-up. Subjects may be followed- up by telephone or contacted by phone to schedule Mount Sinai office visits to monitor for cancer recurrence and or cancer progression in addition to late toxicity.
- If patients are not scheduled for their follow-up visits with Mount Sinai Health System, the study team will call the patient to schedule a visit.
 - If the patient schedules a follow-up at Mount Sinai, appropriate measures will be assessed according to the protocol and data will be recorded.
- If the patient is seeing a physician outside of Mount Sinai Health System, we will request that their labs and physician notes are sent to us.
 - A research coordinator will review and record the outside labs and contact the patients to collect any missing information that can be obtained by phone (i.e. bleeding, incontinence, etc.)
 - A symptomology follow-up form, as well as an IIEF assessment form are attached.
 - If additional information is necessary to assess DLTs or AEs, a coordinator will call the patient and request they schedule a follow up visit at Mount Sinai. If the patient is unable to come in for a follow-up visit, they will be dropped the study.
 - If patients are not responsive after 2 attempts, they will be considered lost to follow up and replaced.

For those with adverse pathologic features: At 1 week post RP+ Civasheet

[Type here]

Protocol Title:	A Phase I Single-Arm Open Label Dose-Escalation Study of CivaSheet with Radical Prostatectomy with or without Adjuvant External Beam Radiation Therapy in Patients with High Risk Prostate Cancer
Principal Investigator Name/Contact Info:	[name]/ [contact]/ [contact]
Primary Contact Name/Contact Info	[contact] [name]
Date Revised:	7/22/2022
Study Number:	GCO#1: 16-1314

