implant, 6 weeks after EBRT, 3 months after EBRT and 6 months after EBRT during the clinic visits, subjects will complete the IIEF to assess baseline erectile function following treatment. Subjects will undergo PSA testing for each follow-up visit. Those without adverse pathologic features not undergoing adjuvant EBRT will complete the IIEF to assess baseline erectile function following treatment and will also undergo PSA testing for each follow-up visit. Also at each follow-up visit or telephone follow up, subjects will be screened for toxicity and complications. The assessments may be done by phone when possible or lab results may be sent by the patient to our EMR if patient has followed up with an outside physician. For all patients, a CT-scan at day 0 (RP+Civasheet implant) will be done for a baseline stability assessment of the Civasheet. For all patients, a one month post-implant CT scan will be done of the pelvis for three purposes. The first purpose will be to perform a post-implant dosimetric analysis of the implanted Civasheet®. The bladder, rectum and any other identifiable structures (small bowel, large bowel or lymph nodes) will be outlined. The delivered dose will be calculated using a dose volume histogram and recorded. The second part of the CT will be to design the post-implant external beam radiation field among those who will undergo adjuvant EBRT. The third part will be to assess the stability of the Civasheet and any changes in position from initial implant. Among those who will undergo adjuvant EBRT, an additional post-implant CT scan at 90 days and 6 months will be done of the pelvis to prove stability of the device/implant method and to assess for cancer recurrence while those not undergoing adjuvant EBRT will not receive this imaging at 90 days and 6 months.

e) Specimen Banking for Future Uses Not Part of This Project:

NA

f) Data Storage, Transmission and Confidentiality:

To ensure data accuracy and completeness, random checks will be done by members of the research team listed in the protocol who are not directly responsible for data collection and entry. Data irregularities and errors will be collected and reported to the . Data collected and stored for current and future research use will include age, gender, [type here]

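### BCR is triggered by one unconfirmed PSA above 0.2 ng/ml with no earliest eligible draw, so a transient or still-falling value stays in the Kaplan-Meier curve as a recurrence

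*SAP*

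**What the plan says.** The SAP's Secondary section gives the event definition: "BCR defined as a post-prostatectomy serum PSA > 0.2 ng/ml will also be assessed for each subject". The analysis follows: "the Kaplan Meier-Method will be used to estimate BCR overall and for each dose group and separately for those receiving vs. not receiving EBRT". It is run "once all subjects have completed the 6 months follow-up after EBRT or 6 months follow-up after Civasheet implant if no EBRT is given". Neither document adds a confirmatory value, a repeat interval, a common assay or laboratory, a first eligible date, or a rule for a value that later falls.

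The protocol settles which PSA values exist:

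- Section 3(d), Follow-Up: "Subjects will undergo PSA testing for each follow-up visit".
- Table 1 (men who receive EBRT), in the row that begins "Other required labs (PSA, testosterone, BMP", is marked before the study, on Day 1, at discharge, at 1 week and at weeks 12, 23 and 35, as the extracted table reads.
- Outside results enter by two routes. For men seen elsewhere, "we will request that their labs and physician notes are sent to us"; in addition, "lab results may be sent by the patient to our EMR if patient has followed up with an outside physician".
- Long-term follow-up is stated twice. One statement is "Subjects will be followed every 6 months after completion of study treatment for 4 years"; the next bullet says yearly over the same 4 years. The text does not say which applies to whom.

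**The concern.** A Kaplan-Meier analysis dates the event at the first qualifying value, and the man then leaves the risk set. A man with 0.25 ng/ml at week 12 and undetectable values at weeks 23 and 35 is a recurrence under this definition, although nothing after week 12 suggests that he recurred.

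Two gaps combine. Without an earliest eligible draw, values taken within days of surgery qualify, as does the week-12 value taken just after EBRT. Without confirmation, any later isolated reading qualifies too, including one from a different laboratory. A start date alone would not close the second gap. Confirmation alone would not close the first, because the discharge and 1-week values are consecutive and could confirm each other.

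At stake is the SAP's only measure of cancer control, reported in groups so small that one event is most of the result.

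**Working it through.** **Inputs from the documents.** There are two dose levels with at most 6 evaluable men each (protocol 3(c)). EBRT starts 6 weeks after surgery and lasts 5 weeks (protocol 3(d); SAP). Table 1 has PSA draws at weeks 12, 23 and 35.

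**Plan's own figure.** 2 × 6 = 12 reproduces the stated maximum. The documents give no BCR rate, event count or precision target to reproduce.

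**Timing.** EBRT ends at week 6 + 5 = 11. The week-12 draw is 12 − 11 = 1 week later. Week 35 is 35 − 11 = 24 weeks after EBRT, so the last men treated have about three draws after EBRT when the analysis is run.

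**Weight of one event.** Crude rate 1/n, with exact (Clopper-Pearson) 95% intervals:

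| Men | No event | One event |
|---|---|---|
| 3 | 0% (0 to 70.8%) | 33.3% (0.8 to 90.6%) |
| 6 | 0% (0 to 45.9%) | 16.7% (0.4 to 64.1%) |
| 12 | 0% (0 to 26.5%) | 8.3% (0.2 to 38.5%) |

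**Chance of a false event under the current definition.** Let f be the chance that one draw gives an isolated false value above 0.2. The documents do not give f; 1 to 5% is an assumption, as is independence between draws. Over three draws, the chance per man is 1 − (1 − f)³:

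- f = 1%: 1 − 0.99³ = 3.0%
- f = 2%: 1 − 0.98³ = 5.9%
- f = 5%: 1 − 0.95³ = 14.3%

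For at least one false event among six men (18 draws), 1 − (1 − f)¹⁸ gives 16.5%, 30.5% and 60.3%.

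**Longer follow-up.** At f = 2%, adding 4 yearly visits gives 7 draws and 1 − 0.98⁷ = 13.2% per man. Adding 8 six-monthly visits gives 11 draws and 1 − 0.98¹¹ = 19.9%. The gap between the two is set by the protocol's conflicting follow-up statements.

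**Same three draws under the fix below.** In the main curve, a false event needs either a false value at week 35 with nothing after it, or false values at both weeks 12 and 23: f + f²(1 − f). In the confirmed-only curve it needs two consecutive false values: 2f² − f³.

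| f | Current | Main curve after fix | Confirmed only |
|---|---|---|---|
| 1% | 3.0% | 1.0% | 0.02% |
| 2% | 5.9% | 2.0% | 0.08% |
| 5% | 14.3% | 5.2% | 0.5% |

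If false readings tend to repeat, confirmation helps less. With 20% repeating and f = 2%, the confirmed-only figure is at most 2 × 0.02 × 0.2 = 0.8%, and the main-curve figure at most 0.02 + 0.02 × 0.2 = 2.4%.

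The discharge and 1-week draws are left out of these sums. Their effect depends on how fast PSA clears after surgery, which the documents do not give.

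**The case against.** The strongest reply is that little depends on this. BCR is secondary and descriptive, has no test attached and does not enter the MTD rule. With six men the intervals for zero and one event overlap almost entirely. That stands, and it fixes the weight of the point.

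The false-reading rate is also an assumption, so the documents cannot show that isolated readings are likely. That stands too. Independence is a further assumption: the causes one would name, a laboratory offset or a PSA still falling, can persist from draw to draw. Positive correlation lowers the per-man chance for a given f and weakens confirmation.

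Confirmation can do harm if done carelessly. Censoring a man because his last PSA is high is informative. It would fall mostly on the later-enrolled 75 Gy men, who have the fewest later draws, and on men who leave the study when progression calls for hormonal therapy (protocol, Withdrawal of Subjects). This objection is right, and the fix avoids such censoring.

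Three stronger readings are tempting, and the documents do not support them:

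- **The 60 Gy men, enrolled first, collect more false events and so bias the dose comparison.** Kaplan-Meier conditions on the men still at risk, so longer follow-up adds events only at later times. Nothing says that 60 Gy men are tested more often at a given time.
- **About one man in five would have a false event (the 11-draw figure).** This takes the six-monthly schedule over the yearly one. It may count week 35 twice, as week 35 falls close to the first six-monthly visit. It also needs 4 years of draws after treatment, in a study expected to take at most 44 months.
- **Nearly every man is an event at the 1-week draw.** The wording admits that draw, but the documents give no PSA clearance rate from which to size the effect.

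Finally, the SAP does not itself say that an event is permanent. That follows from the method and from the absence of any reversal rule.

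**Conclusion.** The point holds as a gap in the endpoint definition. One PSA above 0.2 ng/ml at any draw after surgery, from any laboratory, is a BCR event as written, and a transient or still-falling value remains in the curve. One such event takes a full dose group from 0% to 16.7%. Under an assumed 1 to 5% false-reading rate per draw, independent over three draws, 3.0 to 14.3% of men would have one. The weight of a single event is plain arithmetic on the group size; the probabilities rest wholly on the assumed rate and on independence.

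The effect is confined to the descriptive cancer-control estimate. The MTD determination is untouched, and no bias between doses is shown. This is a worthwhile, inexpensive improvement.

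**What to change.** Amend the SAP's BCR paragraph as follows:

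1. **Eligible draws.** Exclude the discharge and 1-week values. The first eligible draw is week 12 or, for men without EBRT, the first routine follow-up draw.
2. **Event.** PSA > 0.2 ng/ml confirmed by the next available PSA > 0.2 ng/ml, preferably from the same laboratory, and dated at the first of the two.
3. **No later PSA.** If a value above 0.2 is the last one available (cut-off, withdrawal or start of hormonal therapy), count it as an event in the main curve and do not censor it. Only a next value of 0.2 or below cancels it.
4. **Sensitivity curve.** Repeat the analysis with confirmed events only.

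Separately, reconcile the six-monthly and yearly follow-up statements in protocol section 3(d), because they set how many PSA values each man contributes and how long a confirmation can take.

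The endpoint change costs SAP wording only and uses draws already planned. Its downside is that a false rise at a man's last draw still counts in the main curve; the sensitivity curve shows how much that matters.
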